7.1.4.4 Double-blind Maintenance Phase Week 26/Withdrawal (Visit 5.2)

The Double-blind Maintenance Phase Withdrawal Visit may occur at any time the subject discontinues participation in the Double-blind Maintenance Phase, or at completion of the study at Week 26 of the Double-blind Maintenance Phase.

Collection of stool samples for all assessments must occur before administration of any bowel preparations for endoscopy if samples are collected on the same day as bowel preparation administration.

Endoscopy (flexible sigmoidoscopy or colonoscopy) should be performed at Visit 5.2 where possible. If performed, endoscopic videos or photographs will be collected and sent to the study's central endoscopy reader for evaluation of mucosal healing. Please see a description of criteria used for endoscopic scoring in [Appendix 2](#).

Subjects and/or caregivers will have collected UC-DAI symptoms (rectal bleeding and stool frequency) via e-diary once a day before bedtime for 5 days prior to each study visit in the Double-blind Maintenance Phase except for Visit 5, which includes collection and dispensation of investigational product only. The average stool frequency and rectal bleeding scores will be calculated and made available to the investigator through a report from the e-diary provider. The average stool frequency and rectal bleeding scores will be added to the PGA score determined by the investigator to calculate the partial UC-DAI. Please see a description of the PGA in Section [7.2.1.1](#) and the UC-DAI in Sections [7.2.1.1](#) and [7.2.1.2](#).

The IMPACT III (for children aged 8-17 years) and Global Change in Health questionnaires will be completed via paper at Visit 5.2. Please see a description IMPACT III and Global Change in Health questionnaires in Section [7.2.4.1](#).

The PUCAI score will be calculated by a physician at the site, where applicable. Please see a description of the PUCAI in Section [7.2.4.1](#).

A pharmacokinetic sample will be taken with the biochemistry and hematology sample from subjects at sites qualified for and participating in the pharmacokinetic sampling. Please see a description of the pharmacokinetic sampling in Section [7.2.3](#).

See [Table 3](#) for a listing of all Visit 5.2 procedures.

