7.2.1.2 Modified Full UC-DAI Score

The full UC-DAI is widely used to assess treatment efficacy in subjects with mild to moderate UC (Schroeder et al. 1987; Sutherland et al. 1987). It consists of 4 individual parameters: stool frequency, rectal bleeding, endoscopy score (mucosal appearance), and PGA. For the purpose of this study, the standard UC-DAI scale has been modified so that an endoscopy score of mild disease does not include friability; instead, friability will be scored as 2: moderate disease.

Please see a description of stool frequency, rectal bleeding and PGA in Section [7.2.1.1](#).

All 4 parameters will be assessed individually on a scale from 0-3; the maximum total modified full UC-DAI score is 12.0. The modified full UC-DAI score will be calculated at Baseline (Visit 2), Week 8 of the Double-blind Acute Phase (Withdrawal) for subjects not entering into the Open-label Acute Phase, Week 8 of the Open-label Acute Phase (Withdrawal) for subjects who have not had endoscopy at the end of the Double-blind Acute Phase, and Week 26 of the Double-blind Maintenance Phase (Withdrawal) visits. The total score will be calculated by summing the individual scores for the 4 parameters (endoscopy score will be based on the central reader's score). The site is not required to calculate the full UC-DAI; this will be calculated centrally using e-diary and eCRF data.

For determination of the modified full UC-DAI, the average of the symptom scores of the last available 3 days within the 5-day period immediately prior to study visits where endoscopic data are available, will be used. No symptom data older than 5 days prior to the study visit will be used. Data collected on days when bowel preparations have been administered or when endoscopy has been performed will be excluded.

An endoscopy must be performed and mucosal appearance scored within 21 days prior to the Screening Visit (Visit 1), during the Screening period or at the Baseline Visit (Visit 2) depending on the subject's UC history and phase of the study into which they are entering. All efforts should be made to perform endoscopy at Week 8 of the Double-blind Acute Phase (or Week 8 of the Open-label Acute Phase, as applicable), Week 26 of the Double-blind Maintenance Phase, or the subject's withdrawal if different from these visits.

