During this study, an attempt will be made to collect endoscopy data in approximately 30% of subjects at the end of the Acute Phase (combined Double-blind and Open-label) and approximately 30% at the end of the Double-blind Maintenance Phase. In addition, data from endoscopies performed as a part of routine clinical care during a subject's participation in the study will be collected.

Endoscopies will be centrally read and scored for this study, and endoscopic video or photographs must be provided to the central reader for each endoscopy performed. Video images are preferred; however, photographic images will be accepted when video images are not of sufficient quality, as determined by the central reader during individual site image evaluation prior to enrollment at the site. Further details of requirements for video and photographic images will be provided to study sites under separate cover by the central reader. All endoscopies should be performed by the same investigator/endoscopist, if possible, to ensure consistency in endoscopy.

Please see [Appendix 2](#) for the modified full UC-DAI.

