5.8 Analysis of Efficacy

All efficacy analyses will be based on the Safety Analysis Set specific to the study phase. Baseline is defined as the last observation prior to first dose of investigational product in the study. The Double-blind Acute Phase Week 8/Withdrawal visit (Visit 3.2) is treated as the Open-label Acute Phase Week 0 for subjects continuing into the Open-label Acute Phase from this visit. The Double-blind Acute Phase Week 8/Withdrawal visit (Visit 3.2) is treated as the Double-blind Maintenance Phase Week 0 for subjects continuing into the Double-blind Maintenance Phase from this visit. The Open-label Acute Phase Week 8/Withdrawal visit (Visit 4.2) is treated as the Double-blind Maintenance Phase Week 0 for subjects continuing into the Double-blind Maintenance Phase from this visit. For subjects who enter the Double-blind Maintenance Phase directly, the Baseline Visit (Visit 2) is treated as the Double-blind Maintenance Phase Week 0.

The final on treatment assessment (FoTA) for the Double-blind Acute phase is defined as data from the Double-blind Acute phase Week 8, or early withdrawal visit if subject withdrew prior to Week 8. The FoTA for the Open-label Acute phase is defined as data from the Open-label Acute phase Week 8, or early withdrawal visit if subject withdrew prior to Week 8. The FoTA for the Double-blind Maintenance phase is defined as data from the Double-blind Maintenance phase Week 26, or early withdrawal visit if subject withdrew prior to Week 26.

Details of the derivation of the composite endpoints (partial and full UC-DAI scores) are included in Section 8.2.

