5.8.2 Secondary Efficacy Endpoints and Analysis

The secondary endpoints for this study are defined separately for both the Double-blind Acute and Double-blind Maintenance Phases and will be conducted using the appropriate Safety Analysis Set for the phase.

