5.8.2.1 Double-blind Acute Phase

- The proportion of subjects with a clinical and endoscopic response at Week 8, defined as UC-DAI ≤ 2 with rectal bleeding=0 and stool frequency ≤ 1 and PGA=0, and with mucosal healing (endoscopy score ≤ 1) based on central reading. In addition, there must be at least a 1-point reduction in endoscopy score from baseline. This endpoint will be compared between treatment arms using a continuity corrected chi-squared test. If any of the expected cell counts are very low (i.e., less than 5), then Fisher's Exact Test will be used as an alternative analysis method. Subjects with missing data at Week 8 will be assumed not to have had a clinical response. Subjects who completed week 8 but who did not have central reading endoscopies at both baseline and week 8 will be excluded.
- The proportion of subjects with a clinical and endoscopic response at Week 8, defined as UC-DAI ≤ 2 with rectal bleeding=0 and stool frequency ≤ 1 and PGA=0, and with mucosal healing (endoscopy score ≤ 1) based on local reading. In addition, there must be at least a 1-point reduction in endoscopy score from baseline. This endpoint will be compared between treatment arms using a continuity corrected chi-squared test. If any of the expected cell counts are very low (i.e., less than 5), then Fisher's Exact Test will be used as an alternative analysis method. Subjects with missing data at Week 8 will be assumed to be treatment failures. Subjects with missing data at Week 8 will be assumed not to have had a clinical response. Subjects who completed week 8 but who did not have local reading endoscopies at both baseline and week 8 will be excluded.
- The change in the DUCS score from baseline to Week 8 of the Double-blind Acute Phase. This endpoint will be compared between treatment arms using an analysis of covariance (ANCOVA), including treatment arm as a factor and the baseline DUCS score as a covariate in the model.
- The percentage of subjects with an improvement (change of ≥ 20 points) in PUCAI score from baseline to Week 8 of the Double-blind Acute Phase. This endpoint will be compared between treatment arms using a continuity corrected chi-squared test. If any of the expected cell counts are very low (i.e., less than 5), then Fisher's Exact Test will be used as an alternative analysis method. Subjects with missing data at Week 8 will be assumed not to have had a clinical response.

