5.8.2.2 Double-blind Maintenance Phase

- The proportion of subjects who have maintained a clinical and endoscopic response at Week 26, defined as UC-DAI ≤ 2 with rectal bleeding=0 and stool frequency ≤ 1 and PGA=0 and with mucosal healing (endoscopy score ≤ 1) based on central reading. This endpoint will be compared between treatment arms using a CMH test stratifying by Week 8 responder status. Subjects with missing data at Week 26 will be assumed not to have had a clinical response. If there are an insufficient number of subjects with central reading endoscopy data, then the CMH test will not be performed. The number and percentage of subjects with clinical and endoscopic response – based on central response will be presented by treatment arm.
- The proportion of subjects who have maintained a clinical and endoscopic response at Week 26, defined as UC-DAI ≤ 2 with rectal bleeding=0 and stool frequency ≤ 1 and PGA=0, and with mucosal healing (endoscopy score ≤ 1) based on local reading. This endpoint will be compared between treatment arms using a CMH test stratifying by Week 8 responder status. Subjects with missing data at Week 26 will be assumed not to have had a clinical response. If there are an insufficient number of subjects with central reading endoscopy data, then the CMH test will not be performed. The number and percentage of subjects with clinical and endoscopic response – based on local response will be presented by treatment arm.
- The change in the DUCS score from Double-blind Maintenance Phase Week 0 to Week 26. This endpoint will be compared between treatment arms using an analysis of covariance, including treatment arm as a factor, the DUCS score at Double-blind Maintenance Phase Week 0 and Week 8 responder status as covariates in the model.
- The percentage of subjects in remission (PUCAI < 10) at Double-blind Maintenance Phase Week 26. This endpoint will be compared between treatment arms using a CMH test stratifying by Week 8 responder status. Subjects with missing data at Week 26 will be assumed not to have had a clinical response.

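### Week 26 clinical and endoscopic response: with missing data counted as failure and no exclusion of completers who had no endoscopy, the reported percentage can be limited by endoscopy coverage

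*SAP*

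**What the plan says.** SAP 5.8.2.2 defines two Week 26 endpoints, one on central and one on local endoscopy reading. Each needs all the clinical components plus an endoscopy score of at most 1. Both bullets state: "Subjects with missing data at Week 26 will be assumed not to have had a clinical response". On the denominator, SAP 5.8 says "All efficacy analyses will be based on the Safety Analysis Set specific to the study phase", and SAP 5.8.2 repeats that the secondary endpoints "will be conducted using the appropriate Safety Analysis Set for the phase".

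The Week 8 bullets in SAP 5.8.2.1 carry the parallel missing-data sentence and then add a second rule. For central reading: "Subjects who completed week 8 but who did not have central reading endoscopies at both baseline and week 8 will be excluded". For local reading: "Subjects who completed week 8 but who did not have local reading endoscopies at both baseline and week 8 will be excluded". SAP 5.8.2.2 has no counterpart. SAP 7.2 covers missing data for the primary endpoint only, and Protocol 9.8.3.2 gives no missing-data rule for these endpoints.

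On how many subjects will have the examination, Protocol 7.1.4.4 says "Endoscopy (flexible sigmoidoscopy or colonoscopy) should be performed at Visit 5.2 where possible". Protocol 7.2.1.2 says "All efforts should be made to perform endoscopy" at Week 26, among other visits. It also says that collection will be attempted in "approximately 30% at the end of the Double-blind Maintenance Phase", with routine-care endoscopies collected as well. SAP 4.2.1 repeats the wording on effort but gives no number.

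Both Week 26 bullets, and SAP 6, drop the CMH test if central-reading data are too few. No threshold is given, and the number and percentage by arm are still presented.

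For PUCAI, SAP 5.8.2.1 and 5.8.2.2 both treat missing data as non-response. Protocol 7.2.4.1 and SAP 4.3.4 say that only sites holding a sublicense can collect it.

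**The concern.** Counting missing data as failure is a familiar convention when data are missing because a subject withdrew. Here the examination is optional by design. A completer with no bleeding, a stool frequency score of at most 1 and a PGA of 0, but no endoscopy, cannot be shown to meet the endoscopic component and yet stays in the denominator. The percentage then mixes response with endoscopy coverage, and a difference in coverage between arms can look like a difference between doses.

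SAP 3.5 and 5.1 describe an estimation study, so these percentages are themselves the result. The secondary endpoints are also summarized by prior response status and prior treatment (SAP 7.6.2), so eight planned tables inherit the problem (14.2.2.1.5 to 14.2.2.1.12 in SAP 10).

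**Working it through.** The plan gives no assumed response rate, withdrawal rate or precision for these endpoints, so there is no figure to reproduce. From the documents: at least 80 subjects in the phase (SAP 3.5), 1:1 allocation (SAP 3.3), hence 40 per arm at 80, and the target of about 30%. Every other value below is an assumption.

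Notation: *p* is the response rate in the full set if every completer were examined, with withdrawals as failures; *c* is the share of completers examined, unrelated to outcome; *w* is the share withdrawn; *q* is the clinical response rate.

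**1. Unexamined completers counted as failures.** Reported rate = *c* × *p*.

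| *c* | *p* = 70% | *p* = 50% |
|---|---|---|
| 0.3 | 21% | 15% |
| 0.5 | 35% | 25% |
| 0.7 | 49% | 35% |

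The rate cannot exceed *c*. With 80 subjects, no withdrawals, *c* = 0.3 and *p* = 60%, 80 × 0.7 = 56 are unexamined. About 56 × 0.6 = 34 of them are false failures and 56 × 0.4 = 22 are true failures.

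**2. Unequal coverage, *p* = 60% in both arms.** Coverage of 25% v 35% gives 0.25 × 60 = 15% v 0.35 × 60 = 21%. Coverage of 20% v 40% gives 12% v 24%.

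**3. Excluding unexamined completers and keeping withdrawals as failures.** Rate = *cp* / [*c*(1 − *w*) + *w*]; number per arm = 40 × [*c*(1 − *w*) + *w*]. At *c* = 0.3:
- *w* = 0.1: the bracket is 0.37, so 0.21/0.37 = 57% v 0.15/0.37 = 41%, with 14.8 per arm. The 95% half-width for the difference is 1.96 × √[(0.568 × 0.432 + 0.405 × 0.595)/14.8] ≈ 36 points.
- *w* = 0.2: the bracket is 0.44, so 48% v 34%, with 17.6 per arm and a half-width of about 32 points.
- With all 40 per arm examined: 1.96 × √[(0.21 + 0.25)/40] ≈ 21 points.

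This is closer to 70% v 50% than 21% v 15% is, but it is not exact. All withdrawals are kept while most completers are dropped, including known clinical failures. Nor does it remove the effect of unequal coverage: with *p* = 60% in both arms and coverage of 25% v 35%, it gives 46% v 51% at *w* = 0.1 and 38% v 44% at *w* = 0.2.

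**4. Full-set range.** Withdrawals and clinical failures stay failures. Unexamined clinical responders count as all failures (lower limit *cp*) and then all successes (upper limit *q* − *c*(*q* − *p*)). With *q* = 80% v 60% and *p* = 70% v 50%:
- *c* = 0.3: 21–77% v 15–57%
- *c* = 0.7: 49–73% v 35–53%

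The range contains the rate that full examination would have shown in the same subjects, whatever the reason an endoscopy was not done.

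**5. PUCAI.** If a share *u* of subjects is at sites without the sublicense, the reported rate is (1 − *u*) × *p*. For *p* = 80% and *u* = 0, 10, 25 and 50%, that is 80, 72, 60 and 40%. The documents give no value for *u*.

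**The case against.** The best reply is that the missing-data sentence need not reach these completers. The parallel sentence in SAP 5.8.2.1 cannot mean that unexamined completers are failures, because they are then excluded. It also speaks of clinical response, which is known for a completer with diary and PGA data. On that reading SAP 5.8.2.2 has a gap, not a wrong rule. This stands as a point about wording but does not rescue the percentage. Such a subject is still in the Safety Analysis Set and still cannot meet the endoscopic criterion, so counts as a non-responder unless someone excludes them without written authority. The optional missing-data category in SAP 5.1 would show coverage but does not settle the denominator.

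Second, the two phases differ. The Week 8 endpoint needs a fall in endoscopy score from baseline and the Week 26 endpoint does not, and SAP 6 records a separate sparse-data clause for Week 26. A reader might infer from the missing sentence that it was simply forgotten. The documents do not show that. The difference also means that the Week 8 rule, which needs two endoscopies, should not be copied unchanged. Even so, the sparse-data clause removes only a test and leaves the percentages.

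Third, SAP 5.8.3.1 summarizes the full UC-DAI and endoscopy scores by arm for both readings, and subject listings are planned. These make much of the observed data visible. They do not give the composite response rate among those examined.

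Fourth, the repair has limits: the exclusion rule is biased and the range is wide at low coverage. Both are true, which is why the two are proposed together.

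**Conclusion.** The point holds and should be fixed. As written, the Week 26 clinical and endoscopic percentages are limited by endoscopy coverage, on the literal reading and equally if unexamined completers merely stay in the denominator. At low coverage they cannot be read as response rates, and unequal coverage could produce a false difference between doses.

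The sizes rest on assumed response rates and on coverage unrelated to outcome and, except in the unequal-coverage examples, to arm. A reader might infer that the results will be capped at 30%. The documents do not support that: the figure is an attempt target, it stands beside wording that asks for every effort, and routine-care endoscopies add to it. At 70% coverage the understatement is much smaller (49% v 35% for a true 70% v 50%). A reader might also infer that the trial's main conclusions are at risk. They are not: the primary endpoints need neither endoscopy nor PUCAI, and p-values are descriptive (SAP 5.1). The PUCAI gap is real on paper, but its size is unknown and may be nil.

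**What to change.** 1. In both Week 26 endoscopic bullets of SAP 5.8.2.2, adapt the Week 8 approach by requiring only the Week 26 endoscopy of the relevant reading. Exclude completers without it, keep early withdrawals as non-responders, and report the number examined per arm beside the percentage.
2. Always show the full-set range from step 4 of the working beside that result, because the exclusion rule alone over-weights withdrawals and drops known clinical failures.
3. Make the CMH condition in the local-reading bullet, and the matching entry in SAP 6, depend on local-reading data.
4. As a secondary point, restrict the PUCAI denominators in both phases to subjects at sublicensed sites, with missing data counted as failure within that group.

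The cost is SAP wording, some programming and wider intervals: about 36 or 32 points either side at 30% coverage with 10% or 20% withdrawal, against about 21 with all 40 per arm. No extra data need be collected. The SAP must be finalized before unblinding (Protocol 9.4), so the change belongs before then.

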9.8.3.2 Double-blind Maintenance Phase

- The proportion of subjects who have maintained a clinical and endoscopic response at Week 26, defined as UC-DAI ≤ 2 with rectal bleeding=0 **and** stool frequency ≤ 1 **and** PGA=0 **and** with mucosal healing (endoscopy score ≤ 1) based on central reading. This endpoint will be compared between treatment arms using a CMH test stratifying by Week 8 responder status.
- The proportion of subjects who have maintained a clinical and endoscopic response at Week 26, defined as UC-DAI ≤ 2 with rectal bleeding=0 **and** stool frequency ≤ 1 **and** PGA=0, **and** with mucosal healing (endoscopy score ≤ 1) based on local reading. This endpoint will be compared between treatment arms using a CMH test stratifying by Week 8 responder status.
- The change in the DUCS score from Double-blind Maintenance Phase Week 0 to Week 26. This endpoint will be compared between treatment arms using an analysis of covariance, including the DUCS score at Double-blind Maintenance Phase Week 0 and Week 8 responder status as covariates in the model.
- The percentage of subjects in remission (PUCAI < 10) at Double-blind Maintenance Phase Week 26. This endpoint will be compared between treatment arms using a CMH test stratifying by Week 8 responder status.

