6. CHANGES TO ANALYSES SPECIFIED IN THE PROTOCOL

- Changes to the analyses specified in the protocol are as follows: The observed-case sensitivity analysis has been removed from the SAP, since the observed-case analysis would be identical to the complete-case analysis. The model-based imputation method sensitivity analysis has been omitted from the SAP as this study is not powered to detect differences between treatment groups and other sensitivity analysis (LOCF and complete case) intended to examine the robustness of the treatment estimate (under the assumption that the subjects with missing Week 8 or Week 26 results are treatment failures) have been included.
- Statements were added to the SAP to clarify that this is an estimation study intended to provide estimates of clinical response for 2 doses (low and high) across a range of weight groups and not powered to detect differences between treatment groups.
- After agreement with FDA, the sample size for the Double-blind Acute Phase has been reduced to 53 subjects due to difficulties with recruitment.
- Subgroup analyses for the primary endpoint were added to the SAP to explore efficacy by weight group and Week 8 responder status.
- For maintenance phase secondary endpoints, the proportion of subjects who have maintained a clinical and endoscopic response at Week 26, using central reading and using local reading endoscopies, if there are an insufficient number of subjects with central reading endoscopy data, then the CMH test will not be performed. The number and percentage of subjects with clinical and endoscopic response will be presented by treatment arm.
- To conduct psychometric analysis of the DUCS would require more data, and thus will be considered in the future.

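### The CMH test for the local-reading Week 26 endoscopic endpoint is switched off by an unquantified shortage of central readings, which that test does not use

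*SAP*

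**What the plan says.** SAP 5.8.2.2 lists two Week 26 clinical and endoscopic response endpoints. The second requires endoscopic healing as follows: "and with mucosal healing (endoscopy score ≤ 1) based on local reading". Both bullets plan a CMH test stratified by Week 8 responder status, and both then carry the same sentence: "If there are an insufficient number of subjects with central reading endoscopy data, then the CMH test will not be performed". For the local endpoint, what is presented is: "The number and percentage of subjects with clinical and endoscopic response – based on local response will be presented by treatment arm".

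SAP 6 lists the condition as a change from the protocol and covers both endpoints in one clause: "using central reading and using local reading endoscopies, if there are an insufficient number of subjects with central reading endoscopy data". Neither place gives a count, a criterion, a decision date or a person responsible.

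Protocol 9.8.3.2 plans the test for both endpoints without any condition: "This endpoint will be compared between treatment arms using a CMH test stratifying by Week 8 responder status".

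On missing data, SAP 5.8.2.2 says: "Subjects with missing data at Week 26 will be assumed not to have had a clinical response". SAP 5.8.2 places the analysis on the phase's Safety Analysis Set.

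**The concern.** Whether the local-reading test is run depends on how many central readings exist, although the endpoint uses only local readings. If central readings are fewer than local ones, a planned comparison can be dropped for an irrelevant reason. Because the shortage is not quantified, two analysts could follow the SAP faithfully and disagree on whether the test should be run.

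At stake is the pooled, stratified between-arm test for one secondary endpoint.

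**Working it through.** **1. Side-by-side reading.** The documents give no threshold or power figure for this endpoint, so there is no stated number to reproduce.

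| | Acute phase, local endpoint (SAP 5.8.2.1) | Maintenance phase, local endpoint (SAP 5.8.2.2) |
|---|---|---|
| Reader named in the data rule | Local | Central |
| Sparse-data trigger | An expected cell count below 5 | Undefined shortage |
| What then happens | Fisher's exact test | No test |
| Completers without endoscopy | Excluded | No exclusion stated |

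The acute rule is matched to its own reader: "Subjects who completed week 8 but who did not have local reading endoscopies at both baseline and week 8 will be excluded". SAP 6 gives reasons for dropping the observed-case and model-based sensitivity analyses, but none for letting central readings govern a local-reading test. The mismatch looks like a sentence carried over from the central bullet.

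**2. Is the clause likely to come into play?** Inputs: at least 80 maintenance subjects (SAP 3.5) and endoscopy sought in about 30% at the end of maintenance (Protocol 7.2.1.2). 0.30 × 80 = 24 scoped, about 12 per arm. Counts of this size make a judgement of shortage plausible.

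**3. What a shortage does to the test.** Missing counts as non-response and no unscoped completer is excluded, so the comparison stays on about 80 subjects. Few readings reduce the number of responders, not the denominator.

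A standard adequacy check for the asymptotic CMH test is the Mantel-Fleiss criterion. Over strata h, with arm sizes n1 and n2, n = n1 + n2, and m responders:

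MF = min(ΣE − ΣL, ΣU − ΣE), where E = n1·m/n, L = max(0, m − n2), U = min(n1, m). Adequate if MF > 5.

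With equal arms and fewer than half responding in each stratum, E = m/2, L = 0 and U = m. So MF = R/2, where R is the total number of responders, and the criterion needs R above 10.

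Illustrative assumptions: N = 80; strata of 52 direct entrants (80 − 28 expected from the acute phases, SAP 3.5) and 14 + 14 (an assumed even split of the 28); k readings; the stated response rate among those read. R = rate × k.

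| Readings k | R at 50% | MF at 50% | R at 70% | MF at 70% |
|---|---|---|---|---|
| 8 | 4.0 | 2.0 | 5.6 | 2.8 |
| 12 | 6.0 | 3.0 | 8.4 | 4.2 |
| 16 | 8.0 | 4.0 | 11.2 | 5.6 |
| 24 | 12.0 | 6.0 | 16.8 | 8.4 |

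With 24 local readings, the local endpoint meets the criterion at both rates. With 8 or 12 central readings, the central endpoint fails at both; with 16 it fails at 50% and passes at 70%. So the local test can be adequate where the central one is not, and the SAP would still allow it to be cancelled. With k = 24 for both readers the rows coincide and the wrong reference has no effect.

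The local test is not always adequate. With 24 readings, R exceeds 10 only if response among those scoped is above 10/24 = 42%; at 30%, MF = 0.30 × 24 / 2 = 3.6. Adequacy turns on the number of responders, which the SAP's reading count does not capture.

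**The case against.** Several stronger readings are tempting, and the documents do not support them.

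- **That all comparison is lost.** SAP 7.6.2 requires secondary endpoints to be summarized by prior response status, which are the CMH strata. SAP 10 lists local-reading tables by arm and prior response status (14.2.2.1.10) and by prior treatment (14.2.2.1.11 and 14.2.2.1.12), none subject to the condition. For this endpoint SAP 5.8.2.2 promises no pooled difference or interval even when the test is run.
- **That the comparison is on about 24 children.** It is on the full maintenance set, as shown above.
- **That the local endpoint is the designated fallback.** Protocol 7.1.1.1 lets local reading stand in only for the entry criterion and uses the central score for the full UC-DAI. At Week 26 the local endpoint is a parallel one.
- **That the decision will follow sight of the results.** The trigger is a count of readings, which can be judged blinded, and Protocol 9.4 requires the SAP to be final before unblinding. A final SAP without a number still leaves the decision open; that is a gap, not evidence of a post-hoc choice.
- **That many central readings will be missing.** SAP 4.2.1 and Protocol 7.2.1.2 require images of every endoscopy, accept photographs where video is inadequate, and check site image quality before enrollment. The two counts may well be close.

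The last point is the strongest, because with equal counts the wrong reference does nothing. But nothing makes the counts equal: Protocol 4.2 and 7.1.1.1 themselves provide for a central reading being unavailable at entry. The missing threshold matters even with equal counts.

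It is also fair that this is a secondary endpoint in a study declared unpowered (SAP 3.5), with descriptive p-values (SAP 5.1) and no multiplicity adjustment (SAP 7.5).

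**Conclusion.** The point stands in limited form. SAP 5.8.2.2 (second bullet) and SAP 6 make the local-reading CMH test depend on an undefined number of central readings that the test does not use. If central readings are fewer than local ones, a planned comparison could be cancelled for an irrelevant reason. The loss is the pooled stratified test, a descriptive p-value on a secondary endpoint.

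The illustration (MF 6.0 for the local endpoint against 2.0 to 4.0 for the central one at 50% response) rests on assumed response rates, an assumed stratum split, equal arms within strata and assumed reading counts. The documents give no expected rate of unreadable central images. The textual mismatch does not depend on any of these. The correction is worth making because it is specific and nearly free.

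**What to change.** 1. In the second bullet of SAP 5.8.2.2, key the condition to local-reading data.
2. In SAP 6, which covers both endpoints, refer to *central or local reading endoscopy data, respectively*. Simply replacing central by local there would mis-key the central endpoint.
3. In both bullets and in SAP 6, replace the undefined shortage and the no-test outcome by a sparse-data rule fixed before unblinding. One suitable choice is the asymptotic CMH test if the Mantel-Fleiss criterion is met and an exact CMH test otherwise. Other rules would serve if they are numeric and name a fallback. The acute phase's expected-count rule belongs to an unstratified 2×2 table and does not carry over directly.
4. Report the stratified difference between arms with a 95% CI in either case, which suits a study whose stated aim is estimation.

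The cost is a few sentences in the SAP and a small amount of extra analysis work. No data collection changes.
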